### Document History

Document	Version Date	Summary of Changes and rationale
Amendment 1	11 June 2012	
The Schedule of Activities and associated protocol sections were revised to include growth and pubertal maturation assessments for paediatric patients, a reduced mandatory visit schedule after Cycle 3, and clarification of standard tumor analysis requirements.
 
The term “chemotherapy naïve” was removed from the study design and the associated secondary objective to study tolerability in pediatric patients with GIST.
 
Multiple changes were made according the new Pfizer standard safety language for clinical protocols. One significant change in safety language is the following in Section 8.2 Reporting Period: Should an investigator be made aware of any SAE occurring any time after the active reporting period, it must be promptly reported. Previously, this SAE reporting required a potential causal relationship to the study drug.
 
A change in contraception language for the UK was made at the request of the

		
UK regulatory authorities.
 
Administrative changes and clarifications made throughout.

Amendment 2	31 July 2017	
The number of patients to be enrolled in the study (in the range of age from 6 to < 18) has been reduced from 15 to 6 evaluable patients.
 
The centralized review of imaging (ie, MRI, CT scans etc) aimed to confirm the efficacy endpoint is no longer required.
 
As this study is part of a PIP, both these changes above have been agreed with PDCO and are aligned with the PIP binding elements.
 
Rationale for changes are as follow:
 
The primary objective of the study is the characterization of plasma PK profile of sunitinib and its active metabolite in patients with unresectable GIST. A total of six pediatric patients have been included in the study as of today, and the enrollment of additional patient is unlikely due to the rarity of the disease. Recognizing this number is lower than originally planned it still allows the characterization of the pk profile in pediatric patients i.e the analysis of the primary endpoints of the

		
study.
 
In regards to the centralized review of imagine, this is considered no longer necessary due to the small number of patients enrolled, and in absence of PR or CR.
 
The wording related to the reporting of SAE has been aligned with the current protocol template.
 
New text: SAEs occurring to a patient after the active collection period has ended should be reported to the sponsor if the investigator becomes aware of them; at a minimum, all SAEs that the investigator believes have at least a reasonable possibility of being related to investigational product are reported to the sponsor.

Original Protocol	11 October 2011	NA

## PROTOCOL SUMMARY

Gastrointestinal stromal tumor (GIST) is a tumor of mesenchymal origin occurring in the gastrointestinal tract. GIST is a very rare and newly recognized tumor in children. Pediatric GIST has a different clinical behavior and biology than typical adult GIST. The majority of pediatric GIST occurs in females, and these tumors commonly do not bear the genetic mutations present in adults with GIST.

Sunitinib (SUTENT®) received approval from the US FDA and the European Medicines Agency (EMA) in 2006 for the treatment of GIST after disease progression on or intolerance to imatinib mesylate. Following negotiations with the EMA's Pediatric Committee (PDCO), the sponsor (Pfizer) agreed to conduct this single agent, open-label, single arm, multi-centre trial of sunitinib to investigate the use of sunitinib for the treatment of pediatric GIST, collecting safety, pharmacokinetic (PK) and efficacy data in at least 6 children aged 6 years to less than 18 years with a primary endpoint of PK parameters of sunitinib and its active metabolite SU012662.

The primary objective of this study is to characterize the plasma PK profile of sunitinib and its active metabolite SU012662 in children and young adults with advanced, unresectable GIST. Secondary objectives include evaluation of whether doses greater than the established pediatric maximum tolerated dose (MTD) are tolerated in pediatric patients with GIST, and the safety, tolerability, and anti-tumor activity of sunitinib in children and young patients with GIST. The study will explore PK-pharmacodynamic relationships with respect to safety and efficacy if data allows. The primary endpoint will be the PK parameters of sunitinib and its main active metabolite including total plasma exposure (AUC24) and oral clearance (CL/F). Secondary endpoints will include the definition of adverse events and laboratory abnormalities, the objective response rate (ORR), duration of response, progression-free survival (PFS), and the overall survival (OS) at 2 years after study enrollment. Pharmacokinetic-pharmacodynamic relationships with respect to safety and efficacy in pediatric GIST will be detailed, if data allows.

**Study Design:** This study is a single arm, multi-center, multi-national, trial evaluating the PK, safety and preliminary anti-tumor efficacy of sunitinib in children and young adults diagnosed with advanced, unresectable GIST. The study aims to enroll 6 evaluable children aged 6 years to less than 18 years. In addition, up to 15 young adults aged 18 years to less than 21 years may be enrolled. The starting dose of sunitinib in children will be approximately 15 mg/m^2/day for 4 weeks followed by 2 weeks with no study drug, using the MTD established during the pediatric Phase 1 clinical trial conducted by the Children's Oncology Group. Intrapatient dose escalation of sunitinib will be allowed, based on tolerability. Investigators will have the option to access real-time PK results to aid in dosing decisions. Sunitinib dosing for the young adults will follow approved guidelines (per current USPI and SmPC). Study treatment for all patients may continue for up to 18 cycles, equaling approximately 2 years of therapy.

Statistical Plan: Descriptive statistics for observed and dose-corrected (where appropriate) pharmacokinetic data will be reported for all patients with at least one pharmacokinetic observation by presenting the population size, arithmetic mean, standard deviation, percent coefficient of variation (CV%), median, minimum, maximum values. In addition, geometric mean and the 95% confidence interval (CI) for the geometric mean, will be reported where appropriate. Other endpoints, including safety and efficacy endpoints, will be collected, analyzed and presented descriptively.

**Table 1. SCHEDULE OF ACTIVITIES**

The Schedule of Activities table provides an overview of the protocol visits and procedures. Refer to Study Procedures ([Section 6](#)) and Assessments ([Section 7](#)) for detailed information on each procedure and assessment required for compliance with the protocol.

Protocol Activity	Screen <28 days of first dose	Cycles 1-3 (Days 1-42) [23]				Cycles 4-18 [23]		End of Treatment [4]	Follow-up +/- 7 days
		D1 [2] (D-2 to D2)	D15 Visit [3] D12-D18, inclusive	D28 Visit [24] D25-D29, inclusive	Therapy Break D29-42	Day 1 (D-2 to D2)			
Baseline Documentation									
Informed Consent	X								
Tumor characteristics [1]	X								
Medical/Oncologic History [5]	X								
PE including Wt, Ht, Vital Signs, Lansky/ECOG [6]	X	X	X	X		X	X	X[Per 6.3.1 ]	
Baseline Signs/Symptoms	X								
Laboratory Studies									
Hematology & Chemistry [7]	X	X	X	X		X	X	X[Per 6.3.1 ]	
TSH [8]	X	X				Even Cycles Only	X [8]		
Prothrombin time (PT or INR) [8]	X	If clinically indicated.							
Urinalysis [9]	X	Cycles 2-3 only				Cycle 4 Only	X		
Urine Pregnancy Test [10]	X	X				X	X		
Pharmacokinetic Sampling [11]		Cycle 1: Pre-dose and 2,4,6,8 hrs post first dose  Cycles 2&3: Pre-dose	Pre-dose	Pre-dose					
Sunitinib Dosing [12]		X	X	X		X			
Assessments									
Chest radiograph [13]	X	If clinically indicated.							

Protocol Activity	Screen <28 days of first dose	Cycles 1-3 (Days 1-42) [23]				Cycles 4-18 [23]	End of Treatment [4]	Follow-up +/- 7 days
		D1 [2] (D-2 to D2)	D15 Visit [3] D12-D18, inclusive	D28 Visit [24] D25-D29, inclusive	Therapy Break D29-42			
Tumor assessment(s) [14]	X	X prior to the end of Cycle 2				X prior to the end of each even numbered cycle	X	
FDG-PET [15]	X			Cycle 1 Only				
12-lead ECG [16]	X	Cycle 2 Only					X	
ECHO or MUGA Scan [17]	X	Cycle 3 only				Every 3 rd cycle (ie Day 1 of Cycles 6, 9, 12, etc)	X [Per 6.4.1]	
Adverse Events [18]		Throughout study participation						
Study Drug Compliance [19]								
Concomitant Treatments [20]								
Follow-up Survival Monitoring [21]								X
Growth and Pubertal Maturation [22]	X	See footnote [22]					X	

- Tumor characteristics:** Tumor *KIT*, *PDGFRA*, and *BRAF* genotype and succinate dehydrogenase (SDH) protein expression by immunohistochemistry. If some or all of these have not been previously done, tumor specimens may be sent for analysis during screening. For patients with no available, previously collected tumor tissue and incomplete testing information covering all of the above tests, a core biopsy is required, unless, in the opinion of the investigator, a biopsy would create an unacceptable risk to the patient. Refer to [Section 6.1](#) for additional details and exceptions.
- Day 1 Assessments:** Physical examination, hematology, blood chemistry and urinalysis are not required if acceptable screening assessments are obtained within 7 days prior to the start of study treatment without suggestion of clinical deterioration. Day 1 of subsequent cycles may commence up to two days prior to the scheduled Day 1 visit until one day after the scheduled visit (ie, the washout period can be from 12-15 days).
- D15 visit.** Day 15 of Cycle 1 is a mandatory visit, which includes PK, lab tests, and physical exam. For Cycles 2 and 3 a Day 15 visit is required if dose escalation occurs during that cycle, and includes PK, lab tests, and physical exam. Beyond Cycle 3 Day 15 visits will only occur if a dose escalation occurs or as clinically indicated. PK will not be collected at these additional Day 15 visits but lab tests and physical exam will be performed.
- End of Treatment/Withdrawal:** Assessments (See [Section 6.4.1](#)) not required if performed within 1 week of study withdrawal (within the last 8 weeks for radiological tumor assessments).
- Medical/Oncologic History and Demographics:** Includes demographics, oncologic history, history of other diseases (active or resolved), concomitant illnesses, and information on prior cancer treatments including best response observed. Changes in blood pressure medications (new prescriptions, discontinuations, or changes in dose) will also be recorded.

**6. Physical Examination:** Lansky/ECOG Performance Scale (see [Appendix 5](#)) and height for young adults at screening only; Height and weight required at screening and Day 1 of each cycle and at EOT for pediatric patients. Examination of major body systems; vital signs to include temperature, blood pressure (see [Section 5.2.11](#) for guidelines), heart rate and respiratory rate. Abnormal physical examination findings after screening will be reported as adverse events. Patients below the age of 11 who turn 11 while on-study will then require ECOG performance evaluations.

**7. Hematology & Chemistry:** Required safety tests are also listed in [Section 7.2.2](#). These include white blood count with differential, hemoglobin, and platelets; sodium, potassium, chloride, blood urea nitrogen (BUN), serum creatinine, glucose, uric acid, calcium, magnesium, phosphorous, total bilirubin, alanine aminotransferase (ALT), aspartate aminotransferase (AST), alkaline phosphatase, total protein, albumin, amylase, and lipase. At any time after initiation of dosing if liver function tests are abnormal refer to [Section 8.5.2](#) for guidelines. On visits that do not include dispensation of study drug, these tests may be performed by labs outside of the study sites in cases where patient travel to the study clinic is not possible.

**8. TSH** at screen and Day 1 of Cycles 2, 3, and 4, followed by Day 1 of every even cycle (ie, 6, 8, 10 ...etc.) thereafter (see also [Section 6.2](#)). **Prothrombin time: PT or INR** at screening, then as clinically indicated. When performed, the same test should be used.

**9. Urinalysis:** During screening and Cycles 2-4, as clinically indicated and at end of treatment. *Only protein will be captured on the CRF.* If the results of the dipstick test indicate a  $\geq 2+$  proteinuria, then follow-up should be performed with a quantitative urine protein analysis according to local standard practices, with data captured on the AE CRF if AE criteria are met.

**10. Pregnancy Test:** Urine test required for all females above age 11 within 7 days prior to administration of the first dose of sunitinib, on Day 1 of each cycle, and at the end of treatment. Patients of less than 11 yrs at study start who turn 11 while on-study will then require pregnancy testing per the [Schedule of Activities](#). Refer to [Section 7.2.3](#) for details.

**11. PK sampling:** All PK samples collected before and on the Cycle 1 Day 28 Visit should be shipped immediately to BASi Lab for bio-analysis; refer to [Section 7.1](#) for details. Optional Visit Days are C1D7 (D4-D10, inclusive) and C1D21 (D18-D24, inclusive); refer to [Section 7.1](#) for details.

**12. Sunitinib dosing:** Sunitinib will be dosed Days 1-28 of each cycle followed by a 2 week break in therapy. Dosing will be on an outpatient basis except on days when PK sampling is performed. Capsules should be taken once daily in the morning on the first 28 days of each cycle with the exception of study visit days on which the dose for that day should be withheld until immediately after the completion of all study visit day activities and the investigator's approval for continued dosing. See [Section 5.2.3](#) for details.

**13. Chest radiograph** at screening and as clinically indicated. Patients who undergo Tumor Imaging (MRI or CT scan) that includes the chest do not need to have a Chest radiograph performed.

**14. Tumor Imaging:** MRI (or CT scan) of abdomen and pelvis and any other applicable sites of disease at screening, within 14 days prior to the end of each even numbered cycle (Day 28, preferably), whenever disease progression is suspected, to confirm a partial or complete response (at least 4 weeks after initial documentation of response), and at the End of Treatment/Withdrawal (Refer to [Section 7.4](#)).

**15. FDG-PET** at baseline and at the cycle 1 day 28 visit (if locally available; see [Section 7.4](#)).

**16. ECG:** Three consecutive 12-lead ECGs approximately 2 minutes apart will be performed at screening, on Cycle 2, Day 1 and at the end of treatment to determine the mean QTc interval. Attempts should be made for the ECGs to be performed in the morning and time-matched ( $\pm 1$  hour) with screening assessment. ECGs should be done before blood is drawn or 30 minutes afterwards. If the mean QTc interval is prolonged ( $>500$  msec), the ECGs should be read by a cardiologist at the site for confirmation. Additional ECGs may be performed as clinically indicated. ECG should be performed approximately 2 weeks following any sunitinib dose escalation.

**17. Echocardiogram or MUGA scan** at screening, then on Day 1 of every 3rd cycle (for example, Day 1 Cycle 3, Day 1 Cycle 6 ..etc.). As clinically indicated at the end of treatment/withdrawal per [Section 6.3.1](#) and see suggested dose modifications guidelines for left ventricular systolic dysfunction in [Section 5.2.10](#).

18. Adverse Events: Patients must be followed for adverse events from the first day of study treatment until 28 days after the last dose of study treatment, or until all serious or study drug-related toxicities have resolved or are determined to be “chronic” or “stable,” whichever is later. Serious adverse events should be monitored and reported from the time that the patient provides informed consent as described in the protocol.

19. Study Drug Compliance: Unused sunitinib will be returned to clinic for drug accountability at the beginning of each subsequent cycle.

20. Concomitant Medications/Treatments will be recorded from 28 days prior to the start of study treatment, during the study and up to 28 days after the last dose of sunitinib.

21. Follow-up Survival Monitoring: Follow-up survival information, including post-study anti-cancer treatment, will be collected by clinic visit or telephone contact every 3 months until death, or either 24 months from patient’s first dose of study treatment or completion of 18 cycles. See Section 6.3.2.

22. Growth and Pubertal Maturation Assessments (for pediatric patients only): Bone age assessments must be performed at screening, and then annually with an additional test at End of Treatment or until growth plate closure. Tanner staging must be performed at screening. If patient is Tanner Stage 1-4, then Tanner assessment should be repeated every 6-9 months and at End of Treatment or until patient reaches Tanner Stage 5. Refer to Section 7.3 Growth and Pubertal Maturation Assessments. Tanner staging assessments can only be waived upon agreement by Pfizer. If Tanner staging is initiated it should be continued per Section 7.3.


23. Reduced Visit Schedule Following Cycle 3: Following Cycle 3, patients may visit the clinic on Day 1 (within Day 12-15 of the previous sunitinib washout period) of each cycle only or more frequently at the discretion of the investigator. On cycles where there is a dose escalation, a Day 15 visit is required. Labs and physical exam required when visits occur. Sunitinib dosing information will be collected on Day 1 of each cycle and when Day 15 visits occur.

24. Day 28 Visits: Day 28 monitoring for labs at discretion of investigator after Cycle 3.

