### 1.3.2. Sunitinib Pharmacokinetics and Safety in Adult Clinical Trials

In adults, repeated dosing studies over a range of 25-100 mg daily doses followed by off-treatment periods have identified a 50 mg dose on the Schedule 4/2 (4 weeks of therapy followed by a 2-week off period) as a tolerable, dose dense regimen. Steady state levels of sunitinib and its active metabolite SU012662 are reached 7-10 days after repeated daily dosing. Drug accumulation with repeated 4- or 6-week cycles has not been observed. No dose-dependent changes in Tmax or  $t_{1/2}$  have been observed. Sunitinib is metabolized primarily by the cytochrome P450 enzyme, 3A4 (CYP3A4). The terminal elimination half-lives of sunitinib and SU012662 are approximately 40 hours and 80 hours, respectively. Fatigue/asthenia is the primary dose limiting toxicity (DLT); adverse events attributed to sunitinib, independent of treatment schedule have been constitutional (eg, fatigue/asthenia),

gastrointestinal (eg, nausea, vomiting, dyspepsia, diarrhea, stomatitis), dermatologic (eg, dermatitis, skin discoloration, hair depigmentation) and hematologic (eg, neutropenia, thrombocytopenia).

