### 7.2.4. Other Safety Assessments

- Height and body weight will be recorded prior to starting each treatment cycle for pediatric patients.

- Physical examination: A physical examination including, but not limited to, general, lungs, heart, abdomen, and extremities will be performed. The physical examination will include examination of known and suspected sites of disease.
- Performance Status: ECOG performance status scale will be used for patients  $\geq 11$  years of age or Lansky score for patients  $< 11$  years of age. Patients below the age of 11 who turn 11 while on-study will then require ECOG performance evaluations. (Refer to [Appendix 5](#));
- Vital signs: Measurements of temperature, blood pressure, heart rate and respiratory rate after 5 minutes of rest;
  - ECG: Three consecutive 12 lead ECGs (with a 10-second rhythm strip) will be collected approximately 2 minutes apart at screening, on Cycle 2 Day 1 (pre-dose) and at the end of treatment visit to determine the mean QTc interval. It is preferable that the machine used has a capacity to calculate the standard intervals automatically. If the mean QTc interval is prolonged ( $> 500$  msec), the ECGs should be overread by a cardiologist at the site for confirmation. Additional ECGs should be performed as clinically indicated, ie, after a new steady state of sunitinib is reached (ie, approximately 2 weeks) following:
    - Intrapatient sunitinib dose escalation, or
    - Intrapatient sunitinib dose reduction in response to:
      - a. QTc interval prolongation,
      - b. Significant electrolyte changes, vomiting, diarrhea, or addition of a strong CYP3A4 inhibitor listed in [Section 5.5.2](#) after consultation with the sponsor's medical monitor.

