### **9.1.3.5. Electrocardiograms (ECGs)**

Triplicate, 12-lead ECGs are performed at Screening, Day 1 of Cycle 2, and at the end of treatment. At each time point, triplicate data will be averaged and all summary statistics and data presentations will use the triplicate averaged data.

Individual patient ECG data listings will be generated. Changes from baseline in corrected QT (QTc) interval will be calculated to describe and display the frequency of patients who experienced QTc interval prolongation, displayed by category according to CTCAE v4.0 grades. QT intervals will be corrected for heart rate using cube root (Fredericia's) conversion.

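### The one mid-treatment ECG fixed for every patient follows a 12-15 day washout, and SAP 9.1.3.5 can leave the on-drug ECGs out of the QTc table

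*Protocol*

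**What the plan says.** Footnote 16 to the protocol's Schedule of Activities (Table 1) fixes the ECG time points: "Three consecutive 12-lead ECGs approximately 2 minutes apart will be performed at screening, on Cycle 2, Day 1 and at the end of treatment". Section 7.2.4 adds that the Cycle 2 Day 1 recording is taken before dosing: "at screening, on Cycle 2 Day 1 (pre-dose) and at the end of treatment visit to determine the mean QTc interval". On the dosing schedule, Table 1 footnote 12 says: "Sunitinib will be dosed Days 1-28 of each cycle followed by a 2 week break in therapy". Footnote 2 says of later cycles that "the washout period can be from 12-15 days".

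The protocol also asks for further ECGs. Footnote 16 goes on: "ECG should be performed approximately 2 weeks following any sunitinib dose escalation". Section 6.2 extends this to dose adjustments in general. Section 7.2.4 covers escalation and certain reductions, and gives the timing principle: "after a new steady state of sunitinib is reached".

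Section 6.4.1 places the last ECG at end of treatment or withdrawal and waives it if one was done in the last week on treatment. No interval from the last dose is given.

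SAP 9.1.3.5 opens: "Triplicate, 12-lead ECGs are performed at Screening, Day 1 of Cycle 2, and at the end of treatment". It then averages the triplicates, uses those averages for all summaries, and plans a table of the frequency of QTc prolongation by CTCAE grade. It also plans individual ECG listings. Post-dose-change and unscheduled ECGs are not mentioned.

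**The concern.** A table of QTc prolongation is read as a statement about patients taking the drug. Here the one mid-treatment reading that every patient contributes comes at the end of the off-treatment period. If QTc depends on concentration, that reading pulls the change from baseline toward zero.

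The recordings that would show an on-drug effect are those taken about 2 weeks after a dose change, and the SAP does not say whether they count. The protocol excludes proarrhythmic drugs (Section 5.5.1) and allows escalation above the pediatric MTD (Section 5.2.5). With about six children, a table without prolonged QTc could be taken as reassurance when the timing of the ECGs might explain it.

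**Working it through.** **Inputs**
- Cycle of 42 days, dosing on Days 1-28 (Protocol 5.2.3; Table 1 footnote 12).
- Day 1 of a later cycle may fall from two days early to one day late (Table 1 footnote 2).
- Adult half-lives (Protocol 1.3.2): "The terminal elimination half-lives of sunitinib and SU012662 are approximately 40 hours and 80 hours, respectively".
- Pediatric Phase 1 half-lives (Protocol 1.3.5): sunitinib median 38.7 h (range 23.9-61.7); SU012662 median 93.4 h (range 47.4-176).

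**Step 1: reproduce the stated washout.** 42 - 28 = 14 drug-free days. 14 - 2 = 12 and 14 + 1 = 15, which agrees with the protocol's 12-15 days.

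**Step 2: drug remaining at Cycle 2 Day 1.** With first-order decay from the end-of-dosing trough, the fraction remaining is 0.5^(t/half-life), where t runs from 12 × 24 = 288 h to 15 × 24 = 360 h.

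| Analyte and half-life | At 12 days | At 15 days |
|---|---|---|
| Sunitinib, 40 h (adult) | 0.5^7.2 = 0.68% | 0.5^9 = 0.20% |
| Sunitinib, 38.7 h (pediatric median) | 0.58% | 0.16% |
| Sunitinib, 61.7 h (pediatric longest) | 3.9% | 1.7% |
| SU012662, 80 h (adult) | 0.5^3.6 = 8.2% | 0.5^4.5 = 4.4% |
| SU012662, 93.4 h (pediatric median) | 11.8% | 6.9% |
| SU012662, 47.4 h (pediatric shortest) | 1.5% | 0.5% |
| SU012662, 176 h (pediatric longest) | 32% | 24% |

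Counting from the last dose on Day 28 instead (13-16 days) gives 0.37-0.10% for sunitinib and 9.9-5.8% for SU012662 at the pediatric medians. A delayed cycle start under Section 5.2.7 would lower all these values.

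**Step 3: compare with an ECG 14 days into dosing.** The fraction of steady state reached is 1 - 0.5^(336/half-life). At the pediatric medians this is 99.8% for sunitinib and 92% for SU012662.

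**Step 4: which patients have which ECG**
- Cycle 2 Day 1: every patient who reaches it, post-washout.
- About 2 weeks after a dose change: near steady state, but only in patients whose dose changes. Under Section 5.2.8 a child may escalate only without toxicity above Grade 1 in the prior cycle, with listed exceptions, so these ECGs come selectively from children who tolerated the drug.
- End of treatment: on or off drug, unlabelled.
- A child who stays at the starting dose, or a young adult who stays at the flat dose, may have no ECG at steady state. Cycle 1 has a mandatory Day 15 visit and a Day 28 visit, both with pre-dose PK samples, but no ECG is scheduled at either.

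**Step 5: what the SAP table takes in.** SAP 9.1.3.5 names the three fixed time points and uses triplicate averages throughout. The protocol does not say that post-dose-change ECGs are triplicate. A programmer following the SAP literally could leave them out.

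**The case against.** The strongest counter-argument is that the protocol already provides on-drug ECGs. Footnote 16 and Sections 6.2 and 7.2.4 ask for them about 2 weeks after dose changes, and Section 1.3.6 expects most children to qualify for escalation. The end-of-treatment ECG may also fall on drug. This stands. A reader might infer that Cycle 2 Day 1 is the only scheduled on-study ECG, or that the QTc table will largely describe patients with almost no drug on board. The documents support neither. The second depends on how many patients escalate, when end-of-treatment ECGs are taken and which ECGs enter the table, and none of these is settled. Almost no drug is fair for the parent compound but not for the metabolite across its reported half-life range.

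A second argument is that SAP silence is not exclusion. The listings should show each ECG, and a QTc finding that meets the criteria in Protocol 8.4 is also an adverse event, summarised by maximum grade under SAP 9.1.3.1. That limits the harm, since a recorded prolongation need not be lost. It does not tell the reader of the QTc table which patients were ever examined on drug.

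Third, QTc is descriptive safety monitoring here. No exposure-QTc objective is named, and the documents give no QTc effect size. That is fair, and it is why the point concerns how the table is built and labelled, not the validity of the trial.

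**Conclusion.** The concern holds in this form. Cycle 2 Day 1, pre-dose and after 12-15 days off drug, is the only fixed ECG between first dose and end of treatment that applies to every patient. About 0.2-0.7% of sunitinib and 4-12% of SU012662 remain at typical half-lives, and up to 24-32% of SU012662 at 176 h. Patients whose dose never changes may have no steady-state ECG. As SAP 9.1.3.5 is written, the QTc-prolongation table can omit the near-steady-state recordings and mix on-drug with post-washout values, which biases it toward no effect.

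The fractions assume mono-exponential decay from steady state and ignore metabolite formed from residual parent. The direction of bias assumes that any QTc effect follows concentration. Its size cannot be given, because the documents contain no QTc effect and do not fix how many patients will have on-drug ECGs.

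**What to change.** Amend SAP 9.1.3.5:
- Include all post-dose-change and unscheduled ECGs in the maximum post-baseline QTc and CTCAE-category tables, averaged where triplicate and flagged where single.
- Show days since last dose for each ECG, including end of treatment. Dose dates are already recorded in the dosing diary (Protocol 5.2.13). State the rule that classes an ECG as on-drug.
- Present Cycle 2 Day 1 as a post-washout time point, separate from on-drug ECGs.
- Report how many patients had any on-drug ECG, so that absence of a signal is not claimed for patients without one.

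The cost is slightly more programming. Unscheduled ECGs may be single recordings or prompted by symptoms, so they should be identifiable in the table. The SAP still describes the 2011 protocol and 15 children, so it needs revision in any case.

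As a secondary step, for any patient still to start treatment the sponsor could consider scheduling an ECG at an existing on-drug Cycle 1 visit. The reach is small: the protocol's Document History says six children are already included and more are unlikely. If that ECG replaced the one on Cycle 2 Day 1, a pre-dose check would be lost.
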